# 10.7. Pharmacodynamic Variables

## 10.7.1. Primary Pharmacodynamic Endpoint

The primary endpoint of this study is the  $E_{max}$  of Drug Liking VAS.

## **10.7.2.** Secondary Endpoints

In addition to the primary endpoint of change from baseline in  $E_{max}$  of Drug Liking VAS, the following secondary endpoints will be calculated:

- Emax of High VAS
- Emax of Good Effects VAS
- Emax of Bad Effects VAS
- Emax of Sedated VAS
- Emax of Any Effects VAS
- Emax of Desire to use VAS

# 10.8. Drug Concentration Measurements

Venous blood samples (6 mL each) will be collected, as indicated in Table 4. Samples will be collected, processed, and shipped according to instructions provided in the Study MOP. The actual date and time of each blood sample collection will be recorded.

Up to 138 mL of total blood volume will be required from subjects for pharmacokinetic sampling. Analysis of the plasma samples will be detailed in the Study MOP.

Plasma samples will be shipped frozen on dry ice from the research site to the designated bioanalytical laboratory, as outlined in the Study's MOP.

Samples will not be shipped without prior arrangement with the bioanalytical laboratory and/or notification to the Sponsor.

The following pharmacokinetic parameters will be estimated for BPN and norbuprenorphine:

- Cmax (maximum plasma concentration)
- Ctrough (plasma concentration level 7 days after the latest injection)
- Cav (average plasma concentration during a dosing interval).

Details of the pharmacokinetic evaluation will be presented in the SAP.

Version: 2.0, 17NOV2015 Page 67 of 99

# 11. DATA QUALITY ASSURANCE

This study will be conducted under Good Clinical Practice (GCP) and all applicable regulatory requirements. To ensure compliance, the sponsor or designee may conduct a quality assurance audit, as outlined in Section 11.2.

Actions to ensure the accuracy and reliability of data include the selection of qualified investigators and appropriate study centers; the review of protocol procedures with the Investigator and study personnel prior to study start; the design of suitable source documents with appropriate instructions for use (where applicable); the internal audit of source data according to GCP and internal procedures to ensure their accuracy, completeness, and verifiability; as well as the periodic site monitoring by the sponsor. The sponsor or designee will review source documents for accuracy and completeness during on-site monitoring visits and after their return to the sponsor; any discrepancies will be resolved with the Investigator, as appropriate.

Significant and/or repeated non-compliance will be investigated and remedial action instituted when appropriate. Failure to comply with remedial actions may result in investigator site termination and regulatory authority notification.

#### 11.1. Data Collection

Source documents include but are not limited to original documents, data and records such as hospital/medical records (including electronic health records), clinic charts, lab results, subject diaries, data recorded in automated instruments, microfilm or magnetic media, and pharmacy records, etc. This study will use electronic data capture (EDC) or paper CRFs. At a minimum, all data required by the protocol should have supporting source documentation for entries in the EDC system, unless that data can be recorded directly in the EDC system or other device.

All CRFs will be completed by the site staff prior to review by the sponsor's monitor or designated representative. The sponsor's monitor or designated representative will review all source records on-site and compare them to the data collected on the CRF. All entries, corrections, and alterations will be made by the Investigator or other authorized study personnel. All data entries will be verified for accuracy and correctness by independent monitors. The electronic data capture system maintains a full audit trail.

# 11.2. Study Auditing and Monitoring

Monitoring of the study site (including, but not limited to, reviewing CRFs for accuracy and completeness) will be performed by the sponsor's monitor. The extent, nature, and frequency of on-site visits will be based on such considerations as the study objectives and/or endpoints, the purpose of the study, study design complexity, and enrollment rate. By signing the protocol, the Investigator agrees that, within local regulatory restrictions and institutional and ethical considerations, authorized representatives of the sponsor, a regulatory authority, and/or an IRB may visit the site to perform audits or inspections, including the drug storage area, study drug stocks, drug accountability records, subject charts and source documents, and other records

Version: 2.0, 17NOV2015 Page 68 of 99

Braeburn Pharmaceuticals, Inc. CONFIDENTIAL

related to study conduct. The purpose of the sponsor audit or inspection is to systematically and independently examine all study-related activities and documents to determine whether the study-related activities were conducted, and data recorded, analyzed, and accurately reported according to the protocol, the site's standard operating procedures, GCP guidelines of the ICH, and any applicable regulatory requirements. The Investigator should contact the Sponsor immediately if contacted by a regulatory agency regarding an inspection.

Version: 2.0, 17NOV2015 Page 69 of 99

# 12. STATISTICAL METHODS AND DETERMINATION OF SAMPLE SIZE

The following sections describe the statistical methods to be used to analyze the efficacy and safety. These methods may be revised and updated due to reasons such as regulatory requirements or need for further clarifications. The final analysis plan will be documented in a formal statistical analysis plan (SAP) that must be finalized before database lock. The SAP will include details on how variables will be derived, how missing data will be handled, and how data will be presented as well as the details on statistical methods to be used for safety and efficacy analyses. The final clinical study report (CSR) will discuss deviations from the SAP, if any.

# 12.1. Sample Size Determination

A sample size of 24 subjects will provide 90% power for the CAM2038 32 mg to demonstrate no significant difference in the mean  $E_{max}$  score of the Drug Liking VAS comparing to 0 mg hydromorphone at a two-sided 0.05 significance level with a non-significant difference cutoff at  $\leq 11$  points. In the sample size calculation it was assumed that the true difference was less than or equal to 1.5 and the standard deviation was 9.8.

An additional group of 24 subjects will be enrolled to CAM2038 24 mg group. This sample size will provide approximately 83% power for the CAM2038 24 mg to demonstrate no significant difference in the mean  $E_{max}$  score of the Drug Liking VAS comparing to 0 mg hydromorphone at a two-sided 0.05 significance level with a non-significant difference cutoff at  $\leq$  11 points. In the sample size calculation it was assumed that the true difference was less than or equal to 2.5 and the standard deviation was 9.8.

The plan will be to enroll a sufficient number of subjects to ensure that at least 48 subjects complete the study (24 subjects per treatment group) by over-enrollment as needed and replacement of subjects for those who drop out.

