#### 12.3.3.1. Primary Efficacy Analyses

The primary efficacy variable will be  $E_{max}$  of Drug Liking VAS. This variable will be analyzed via a mixed model including subject, challenge dosing (A=0 mg, B=6 mg, or C=18 mg), Period (1, 2, or 3 to indicate first, second, or third day of each challenge session), challenge session (1, 2, 3, or 4), where subject will be treated as random effects and the remaining parameters fixed effects. The estimated treatment effects, differences in treatment effects (test dose – the reference

Version: 2.0, 17NOV2015 Page 71 of 99

dose of 0 mg), 95% confidence intervals of the differences will be presented. Blockade effects will be claimed if upper bound of the treatment difference is  $\leq 11$ .

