# **12.3.6.** Multiple Comparisons

To control for multiple comparisons in the efficacy analyses, the treatment differences between Treatments B (hydromorphone 6 mg) and A (0 mg) will be tested at first at a 0.05 significance level, followed by the tests between Treatments C (18 mg) and A. Blockade effects for hydromorphone 18 mg cannot be claimed unless the blockade effects for 6 mg are established first.

Furthermore, the above tests will be performed for CAM2038 q1w 32 mg first followed by the tests for CAM2038 q1w 24 mg. To control for the Type I error rate, opioid agonist blocking effects for CAM2038 q1w 24 mg cannot be claimed unless blocking effects for CAM2038 q1w 32 mg are established.

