9.1.2 PRIMARY ANALYSIS

The primary analysis of the primary efficacy variable, E_{\max} of drug liking VAS, will be performed using the completer population. This variable will be analyzed via a mixed model including sequence (ABC, ACB, BAC, BCA, CAB, CBA), dosing (challenge dosing A=0 mg, B=6 mg, or C=18 mg), period (1, 2, or 3 to indicate first, second, or third day of each challenge session), session (challenge session 1, 2, 3, or 4), and dosing-by-session interaction as fixed effects, and subject as random effects. The maximum likelihood estimation will be used to estimate the parameters. Specifically, the following pseudo SAS codes will be used for the analysis:

```
proc mixed data=Efficacy_Data method=ml;
class SubjectID ChallengeDose Sequence Period Session;
model Emax=Sequence ChallengeDose Period Session ChallengeDose*Session;
random SubjectID / Subject= SubjectID;
LSMEANS ChallengeDose*Session/diff cl alpha=0.05;
Run;
```

The estimated treatment effects, differences in treatment effects (test dose – the reference dose of 0 mg), 95% confidence intervals of the differences will be presented. Blockade effects will be claimed if the upper bound of the treatment difference is ≤ 11 .

The same methodology will be used to analyze CAM2038 q1w 24 mg and 32 mg separately.

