9.4 ADJUSTMENTS FOR MULTIPLICITY

The study involves multiple comparisons. Procedures will be used to control for the overall Type I error rate at the significance level of 0.05. The following ordered comparisons of blocking effect will be tested at the 0.05 level of significance:

1. Hydromorphone 6 mg vs Hydromorphone 0 mg for CAM2038 q1w 32 mg;
2. Hydromorphone 6 mg vs Hydromorphone 0 mg for CAM2038 q1w 24 mg;
3. Hydromorphone 18 mg vs Hydromorphone 0 mg for CAM2038 q1w 32 mg;
4. Hydromorphone 18 mg vs Hydromorphone 0 mg for CAM2038 q1w 24 mg;

Blockade effect cannot be claimed unless all preceding blocking effects, if any, are established.

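### The 83% power given for CAM2038 24 mg is a per-contrast figure that leaves out the 32 mg gate; on the same planning basis the first 24 mg claim has about 75–76%

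*Protocol*

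**What the plan says.** Protocol 12.1, the synopsis and SAP 9.6 carry the same calculation. Each CAM2038 group has 24 completers, the test is at two-sided 0.05, and blockade means that the upper 95% bound for the difference in Drug Liking Emax from 0 mg hydromorphone is at most 11. For 32 mg the assumed true difference is at most 1.5, the SD is 9.8 and the power is 90%. For 24 mg: "This sample size will provide approximately 83% power for the CAM2038 24 mg to demonstrate no significant difference", where "the true difference was less than or equal to 2.5 and the standard deviation was 9.8". None of the three places mentions the testing order.

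Protocol 12.3.6 sets the order by CAM2038 dose: "the above tests will be performed for CAM2038 q1w 32 mg first followed by the tests for CAM2038 q1w 24 mg", with hydromorphone 6 mg before 18 mg within each dose. It adds: "opioid agonist blocking effects for CAM2038 q1w 24 mg cannot be claimed unless blocking effects for CAM2038 q1w 32 mg are established". SAP 9.4 interleaves the tests: 32 mg with 6 mg, 24 mg with 6 mg, 32 mg with 18 mg, 24 mg with 18 mg. Its rule is: "Blockade effect cannot be claimed unless all preceding blocking effects, if any, are established".

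SAP 9.1.2 says of the two groups: "The same methodology will be used to analyze CAM2038 q1w 24 mg and 32 mg separately". Its code requests dose differences within each session: "LSMEANS ChallengeDose*Session/diff cl alpha=0.05". The model in Protocol 12.3.3.1 has session only as a main effect: "challenge session (1, 2, 3, or 4), where subject will be treated as random effects and the remaining parameters fixed effects".

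**The concern.** The 83% is printed as the power of the 24 mg group to demonstrate blockade. Under either testing order that group cannot support a claim by itself, because at least one 32 mg test must succeed first. The probability of a 24 mg claim is therefore smaller than the probability that the 24 mg contrast meets the margin, and only the latter is stated. A reader who takes 83% as the chance of a 24 mg claim overstates it on the plan's own terms. The size of the overstatement cannot be fixed from the documents, because they do not say what the SD of 9.8 measures, which hydromorphone dose is powered, or which session contrast or contrasts a claim needs.

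**Working it through.** **Inputs** (Protocol 12.1, same in SAP 9.6): n = 24 per group; margin 11; one-sided 0.025, from the upper bound of a 95% interval; true difference Δ = 1.5 (32 mg) and 2.5 (24 mg); SD 9.8.

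**Reproducing the stated figures.** SE = 9.8·√(2/24) = 2.829. Power is the probability that a noncentral t variable with noncentrality (11 − Δ)/SE exceeds the 0.975 quantile of t. The noncentralities are 9.5/2.829 = 3.36 (32 mg) and 8.5/2.829 = 3.00 (24 mg).

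| Error df | 32 mg | 24 mg | Product |
|---|---|---|---|
| 23 (paired, difference SD 9.8·√2) | 0.895 | 0.820 | 0.735 |
| 44 (crossover, one session) | 0.907 | 0.836 | 0.759 |
| 46 (two-sample) | 0.908 | 0.837 | 0.760 |
| 251 (one session contrast, SAP model) | 0.917 | 0.849 | 0.779 |
| Printed figures | 0.90 | 0.83 | 0.747 |

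A two-sample equivalence calculation within ±11 gives 0.899 and 0.834, product 0.749. The printed 90% and 83% are therefore stand-alone powers for one contrast with this SE.

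**Applying the gate, SAP order.** The groups contain different subjects and are modelled separately, so the probabilities multiply. The first 24 mg claim (6 mg vs 0 mg) is second in line: 0.907 × 0.836 = 0.76, or 0.90 × 0.83 = 0.75.

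**Applying the gate, Protocol order.** If both 32 mg tests must pass first, the joint 32 mg probability is needed. With a shared 0 mg mean and residual variance, and Δ = 1.5 assumed for 18 mg as well as 6 mg, simulation at df 44 gives 0.845. Then 0.845 × 0.836 = 0.71 (0.68 at df 23, 0.73 at df 251).

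**Changing what the documents leave open** (24 mg with 6 mg, gated in the SAP order):

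| Assumption | 32 mg alone | 24 mg alone | Gated |
|---|---|---|---|
| 9.8 is a total SD, within-subject correlation 0.1, df 44 | 0.933 | 0.872 | 0.81 |
| Same, correlation 0.2 | 0.956 | 0.907 | 0.87 |
| Same, correlation 0.5 | 0.996 | 0.986 | 0.98 |
| 9.8 is the SD of the paired difference (SE 2.000, df 23) | 0.995 | 0.982 | 0.98 |
| SE 2.829, df 251, all four SAP session contrasts must pass | 0.71 | 0.52 | 0.37 |
| SE 2.829, df 44, true differences 0.5 and 1.5 | 0.952 | 0.907 | 0.86 |

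The first three rows use SE = 9.8·√(2(1 − r)/24). The correlations are assumptions; the documents give none. Pooling four sessions, as the Protocol model would, with 9.8 as residual SD gives SE = 9.8·√(2/96) = 1.415 and gated power above 0.999.

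**The case against.** The strongest reply is that nothing is miscalculated. Per-hypothesis power is often reported beside a fixed-sequence procedure, and the sample size sections never call 83% the probability of passing the sequence. That stands: a reader might infer an arithmetic error, and there is none. What remains is that the figure is unlabelled and is worded as the group's power to demonstrate blockade, which the testing rules make conditional.

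The second reply is that 76% is no more the trial's real power than 83% is. This also stands. The two-sample reading reproduces the printed figures, and on it 9.8 may be a total SD with the pairing ignored at planning. The actual comparison is within subject, so a correlation of 0.2 already lifts gated power to 87%, above the printed 83%. A reader might therefore infer that the 24 mg group is underpowered; the documents do not support that.

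Nor can the gated figures be read as a floor because the true differences are upper limits. If a claim needs all four session contrasts, gated power falls to about 37%.

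A reader might also infer that the 90% for 32 mg is untouched by gating. That is so only if the powered contrast is 6 mg vs 0 mg. If it is 18 mg vs 0 mg, the 90% is gated too, and the dose is not stated.

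Finally, Protocol section 12 leaves the final analysis plan to the SAP, so the 71% for the Protocol order carries less weight than the 75–76%.

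**Conclusion.** The point holds as one of labelling and completeness. The 83% is an ungated, per-contrast power printed as the 24 mg group's power to demonstrate blockade, and both documents bar a 24 mg claim until 32 mg succeeds. On the basis that reproduces the plan's own numbers, with independent groups and true differences at their limits, the first 24 mg claim has about 75–76% in the SAP order, some 7 to 8 points below the printed figure. It has about 71% if both 32 mg tests must pass first and 18 mg has the same true difference as 6 mg. That the gate is omitted is certain. Its effect on the trial's actual power is not known, because it turns on the meaning of 9.8, the powered hydromorphone dose and the session rule.

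**What to change.** In Protocol 12.1, the synopsis and SAP 9.6:

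1. Label 90% and 83% as power per contrast before the gate.
2. Beside them, state the gated 24 mg power for the SAP 9.4 order, about 75–76% on the stated basis.
3. State what the SD of 9.8 measures, and which hydromorphone dose and which session contrast or contrasts the power refers to. If 9.8 is not the SD that belongs in 9.8·√(2/24), recompute both per-contrast figures and the gated one.

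The cost is a short calculation and rewording in three places. Sample size, margin and enrolment do not change. On the basis that reproduces the printed figures, the 24 mg number becomes less favourable. If 9.8 proves to be a total SD with positive within-subject correlation, or a paired-difference SD, the per-contrast figures rise instead.

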# 12.2. Analysis Populations

Three populations are defined for the study:

- Intent-to-treat (ITT) Population will consist of all subjects who receive study drug and provide some post baseline efficacy values.
- Completer Population will include all subjects who complete the study (i.e., complete Day 14). The primary efficacy analyses will be based on the Completer Population.
- Safety Population will include all subjects who receive study drug. All safety analyses will be based on the Safety Population.

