### Name of Investigational Product:

CAM2038 q1w (buprenorphine FluidCrystal® once-weekly subcutaneous (SC) injection depot)

Name of Active Ingredient: buprenorphine (BPN)

<=11 points. In the sample size calculation, it was assumed that the true difference was less than or equal to 1.5 and the standard deviation was 9.8.

An additional 24 completed subjects will be enrolled to CAM2038 24 mg group. This sample size will provide approximately 83% power for the CAM2038 24 mg to demonstrate no significant difference in the mean  $E_{max}$  score of the Drug Liking VAS comparing to 0 mg hydromorphone at a two-sided 0.05 significance level with a non-significant difference cutoff at <=11 points. In the sample size calculation it was assumed that the true difference was less than or equal to 2.5 and the standard deviation was 9.8.

The plan will be to enroll a sufficient number of subjects to ensure that at least 48 subjects complete the study (24 subjects per treatment group) by over-enrollment as needed and replacement of subjects for those who drop out.

Three populations are defined for the study.

- Intent-to-treat (ITT) Population will consist of all subjects who receive study drug and provide some post-baseline efficacy values.
- Completer Population will include all subjects who complete the study (i.e., complete Day 14). The primary efficacy analyses will be based on the Completer Population.
- Safety Population will include all subjects who receive any SC dose of CAM2038. All safety analyses will be based on the Safety Population.

The primary efficacy variable will be  $E_{max}$  of Drug Liking VAS. This variable will be analyzed via a mixed model including subject, hydromorphone challenge dose (A=0 mg, B=6 mg, or C=18 mg), Period (1, 2, or 3 to indicate first, second, or third day of each challenge session), challenge session (1, 2, 3, or 4), where subject will be treated as random effects and the remaining parameters fixed effects. The estimated treatment effects, differences in treatment effects (hydromorphone test dose – the reference dose of 0 mg), and 95% confidence intervals of the differences will be presented. Blockade effects will be claimed if upper bound of the treatment difference is <=11.

Safety analyses will be based on the evaluation of reported adverse events or laboratory outcomes.

Version: 2.0, 17NOV2015 Page 17 of 99

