
The overall design of the current study is consistent with previously published opioid agonist challenge studies, which have investigated the opiate blocking effects of BPN (Jasinski et al., 1978; Walsh et al., 1995). Based on the pharmacokinetic profile of CAM2038 q1w, specifically that BPN peak plasma concentrations are observed within the first 24 hours post-dose,

Version: 2.0, 17NOV2015 Page 42 of 99

Hydromorphone Challenge Sessions will begin a minimum of 24 hours following the first dose of CAM2038 q1w. An additional Hydromorphone Challenge Session will be administered after 48, 72, 96, 120, and 144 hours post-dose in order to investigate the full duration and magnitude of opioid-blockade of the CAM2038 q1w formulation. In order to improve subject retention, the study drug will be administered for two weeks with two sets of three Hydromorphone Challenge Sessions per week; thereby reducing the inpatient Treatment Phase and the overall duration of the study.

In the current study, subjective "at the moment" assessments using VAS for Drug Liking, Feeling High, Any Drug Effects, Good Drug Effects, Bad Drug Effects, Sedated, and Desire to Use Opioids will be included to measure the degree and time course of the CAM2038 q1w-induced blockade of subjective effects. In addition, pharmacokinetic samples will be collected on each Hydromorphone Challenge Session day to measure plasma levels of BPN and norbuprenorphine prior to the challenge session.

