#### 9.2.1. Handling, Storage, and Accountability

All study drugs will be transported, received, stored, and handled strictly in accordance with the container or product label, the instructions provided to the research site, and applicable regulations.

CAM2038 products must be stored according to the requirements outlined in the Study MOP. Storage requirements for hydromorphone are provided in the product label (a copy is provided in the Study MOP).

Detailed drug accountability records must be maintained, including the dates shipments are received, the quantity of material received, the dates dispensed, the running inventory, and the unused quantities returned to the Sponsor's drug supply vendor at the end of the trial. All unused supplies will be checked against the drug accountability records during the study and/or at the end of the study. Additional details are provided in the Study MOP.

Buprenorphine (Schedule III), morphine sulfate and hydromorphone (Schedule II) are controlled substances and study drugs must be handled and stored strictly in accordance with restrictions related to controlled substances. Study drugs must be kept securely locked with access limited to appropriate study personnel, according to applicable regulations.

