#### 12.3.4.1. Adverse Events

Adverse events will be coded by system organ class (SOC) and preferred term using the Medical Dictionary for Regulatory Activities (MedDRA) reporting system. Treatment-emergent AEs are defined as any of the following:

- Non-serious AEs with onset on the date of first dose of treatment with the study drug through discharge or Early Termination, whichever occurs first;
- Serious AEs with onset on the date of first dose of treatment with the study drug through 30 days after discharge or Early Termination, whichever occurs first;
- AEs that start before the start of treatment but increase in severity or relationship at the time of or following the start of treatment through discharge or Early Termination, whichever occurs first.

The number and percentage of subjects with TEAEs will be displayed for each treatment group. During the Qualification Phase subjects TEAEs will be displayed by IR morphine 30 mg

Version: 2.0, 17NOV2015 Page 72 of 99

treatment or by hydromorphone treatment groups i.e., 0 mg 6 mg or 18 mg - on the days of hydromorphone challenges. During the Treatment Phase, TEAEs will be displayed by CAM2038 q1w relevant dose and hydromorphone relevant dose i.e., 0 mg 6 mg or 18 mg - on the days of hydromorphone challenges. TEAEs will be displayed by SOC and preferred term. Additionally, TEAEs will be tabulated for each treatment group by severity and by relationship to the study drug. A listing of SAEs will be provided if applicable.

If an AE is considered to be caused by a drug, the Investigator will note which drug caused the AE.

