5.0 ANALYSIS POPULATIONS

Three populations are defined for the study. Intent-to-treat (ITT) population will consist of all subjects who receive study drug and provide some post baseline efficacy values. Completer population will include all subjects who complete the study. The primary efficacy analyses will be based on the Completer population. Safety population will include all subjects who receive study drug. All safety analyses will be based on the Safety population.

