TABLE 14.2.11.1b	Summary of Change from Baseline in Objective Opioid Withdrawal Scale (OOWS) for CAM2038 24 mg (Completer Population)
TABLE 14.2.11.2a	Summary of Change from Baseline in Objective Opioid Withdrawal Scale (OOWS) for CAM2038 32 mg (ITT Population)
TABLE 14.2.11.2b	Summary of Change from Baseline in Objective Opioid Withdrawal Scale (OOWS) for CAM2038 24 mg (ITT Population)
TABLE 14.2.12.1a	Summary of BPN and norpuprenorphine Concentrations for CAM2038 32 mg (Completer Population)
TABLE 14.2.12.1b	Summary of BPN and norpuprenorphine Concentrations for CAM2038 24 mg (Completer Population)
TABLE 14.2.12.2a	Summary of PK Parameters for CAM2038 32 mg (Completer Population)

TABLE 14.2.12.2b	Summary of PK Parameters for CAM2038 24 mg (Completer Population)
TABLE 14.3.1	Summary of CAM2038 Exposure (Safety Population)
TABLE 14.3.2	Summary of All Adverse Events by System Organ Class, Preferred Term, and Relationship to Hydromorphone During Qualification Period (Safety Population)
TABLE 14.3.3.1	Summary of All Adverse Events by System Organ Class, Preferred Term, and Intensity for CAM2038 Doses and Overall (Safety Population)
TABLE 14.3.3.1.2	Summary of All Adverse Events by System Organ Class, Preferred Term, and Intensity for Hydromorphone and CAM2038 24 mg (Safety Population)
TABLE 14.3.3.1.3	Summary of All Adverse Events by System Organ Class, Preferred Term, and Intensity for Hydromorphone and CAM2038 32 mg (Safety Population)
TABLE 14.3.4.1.1	Summary of All Adverse Events by System Organ Class, Preferred Term, and Relationship to Study Drug for CAM2038 Doses and Overall (Safety Population)
TABLE 14.3.4.1.2	Summary of All Adverse Events by System Organ Class, Preferred Term, and Relationship to Study Drug for Hydromorphone and CAM2038 24 mg (Safety Population)
TABLE 14.3.4.1.3	Summary of All Adverse Events by System Organ Class, Preferred Term, and Relationship to Study Drug for Hydromorphone and CAM2038 32 mg (Safety Population)
TABLE 14.3.5	Summary of All Suspected to Be Drug Related Adverse Events by System Organ Class and Preferred Term for CAM2038 Doses and Overall (Safety Population)
TABLE 14.3.6	Summary of Most Common (at least 5%) Adverse Events by System Organ Class and Preferred Term for CAM2038 Doses and Overall (Safety Population)
TABLE 14.3.7	Summary of All Serious Adverse Events by System Organ Class and Preferred Term for CAM2038 Doses and Overall (Safety Population)

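### The Safety Population is defined in two ways, and on the CAM2038 reading the Qualification adverse event table omits every subject given hydromorphone who did not go on to CAM2038

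*Protocol*

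**What the plan says.** The protocol synopsis (Statistical Methods) says: "Safety Population will include all subjects who receive any SC dose of CAM2038". Protocol 12.2 says: "Safety Population will include all subjects who receive study drug". SAP 5.0 follows 12.2: "Safety population will include all subjects who receive study drug". Protocol 12.2 then gives the set its scope: "All safety analyses will be based on the Safety Population".

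SAP Appendix A lists Table 14.3.2, whose title ends "Relationship to Hydromorphone During Qualification Period (Safety Population". Most of the later adverse event tables use the same population and are laid out by CAM2038 dose and Overall.

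Protocol 8.3 lists five criteria that must all be met before the Treatment Phase. Three concern Drug Liking responses (to 6 mg, 18 mg and placebo), one is tolerance of both active hydromorphone doses, and one is general behaviour. Under Protocol 7.1.2.1, subjects who do not qualify are discharged without CAM2038.

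**The concern.** Two programmers could build different safety flags from this text, and each could cite the plan. The choice matters because every subject receives IR morphine, and is scheduled for the three-day hydromorphone challenge, before anyone receives CAM2038. Entry to the CAM2038 phase depends in part on how the subject reacted to hydromorphone.

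There is no placebo depot arm. Protocol 7.2 gives the Qualification session the job of showing what happens without CAM2038. Safety of CAM2038 given together with hydromorphone is a secondary objective, so the Qualification adverse event table is the natural descriptive reference for it. A table limited to subjects who passed a tolerability criterion is a selected reference, and nothing in its title tells the reader so.

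**Working it through.** No stated figure is at stake, so the check compares the current texts and then traces who is counted. It does not rely on the protocol's summary of changes.

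**1. What study drug covers.**
- Broad use, Protocol 9.2.1: "Buprenorphine (Schedule III), morphine sulfate and hydromorphone (Schedule II) are controlled substances and study drugs must be handled and stored strictly".
- Broad use implied, Protocol 12.3.4.1: the treatment-emergent window covers "Non-serious AEs with onset on the date of first dose of treatment with the study drug", and the same section displays Qualification events as treatment-emergent by IR morphine and hydromorphone dose. Those events come before CAM2038, so the text works only if study drug includes the earlier products.
- Narrow use, Protocol 7.2: "the study drug will be administered for two weeks", which fits only the two weekly CAM2038 injections.
- Narrow use, SAP 11.1: exposure to study drug is measured by the number of injections received, and Table 14.3.1 is titled as CAM2038 exposure.

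The term therefore does not settle which definition applies.

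**2. Who is counted on the CAM2038 reading.** A subject who fails any criterion in Protocol 8.3 gets no CAM2038, is outside the Safety Population, and so is outside Table 14.3.2. The same holds for a subject who qualifies but does not meet the COWS requirement for Day 0 dosing (Protocol 7.1.3.1). Protocol 10.6.1 also excludes from further participation anyone with a hypersensitivity reaction, which it equates with a serious adverse event, after any of the drugs. A hydromorphone reaction that the investigator judges not tolerable during Qualification thus removes the subject, and with the subject the event, from the table.

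**3. How many (illustration).** Inputs: 48 planned completers (Protocol synopsis and 12.1), used as a stand-in for the number reaching CAM2038, and a qualification failure rate f, which the documents do not give. Subjects given hydromorphone = 48/(1 − f), rounded up; omitted = that number − 48.

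| Assumed f | Given hydromorphone | Omitted |
|---|---|---|
| 10% | 54 | 6 |
| 20% | 60 | 12 |
| 30% | 69 | 21 |
| 40% | 80 | 32 |
| 50% | 96 | 48 |

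Planned over-enrolment and replacement mean that more than 48 may receive CAM2038. The omitted number then scales as (number treated) × f/(1 − f).

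**4. Which way the rate moves.** Suppose 5 of the 48 retained subjects had a given event, so the table shows 5/48 = 10.4%. The rate among everyone given hydromorphone would be:
- f = 20%, 12 omitted: 5/60 = 8.3% if none of the 12 had it, (5 + 3)/60 = 13.3% if a quarter did, (5 + 6)/60 = 18.3% if half did.
- f = 50%, 48 omitted: 5/96 = 5.2% if none did, (5 + 12)/96 = 17.7% if a quarter did, (5 + 24)/96 = 30.2% if half did.

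The table understates an event only if it is more common among the omitted subjects. That follows for events that cause the failure. It does not follow for the rest.

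**5. The broad reading.** Everyone given morphine or hydromorphone enters the Safety Population. A subject who did not qualify has no assigned CAM2038 dose, so the 24 mg and 32 mg columns keep their denominators. The Overall column could take these subjects in: at f = 20%, 60 in place of 48.

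**The case against.** The strongest reply is that there is no real conflict. The synopsis lists CAM2038 as the investigational product and places hydromorphone and morphine under reference therapy. SAP 11.1 ties study drug to injections, and SAP 7.1 counts randomized subjects in each population by CAM2038 arm. Read this way, Protocol 12.2 and SAP 5.0 agree with the synopsis. This is a fair reading and probably the easiest to adopt. It removes the conflict but leaves the omission from Table 14.3.2 in place under every definition.

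A second reply is that restricting to CAM2038-treated subjects gives the like-for-like comparison, since the same people are seen before and after CAM2038, and that no formal safety comparison is planned (Protocol 12.3.4; SAP 11.0). That supports showing such a subset. It does not support presenting it, unlabelled, as the only summary of adverse events during the Qualification challenge.

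A reader might also infer that the omitted subjects' events are lost. The documents do not support that. Adverse events are recorded from consent (Protocol 10.4.1.1), SAP 6.0 says listings present all collected data, and the adverse event listings in Appendix A carry no population restriction. The gap is in the summary table and its denominator.

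**Conclusion.** The point holds, at moderate size. The current texts define the Safety Population in two ways. On the CAM2038 reading, Table 14.3.2 under-represents hydromorphone intolerance because tolerance is a condition of entering the population. This part rests on the documents alone. The count of 6 to 48 omitted per 48 retained rests on assumed failure rates of 10% to 50% and shows scale only.

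Two stronger readings are tempting and should not be made. A reader might infer that all Qualification adverse event rates are biased low. The documents do not show this: three of the five criteria concern Drug Liking or placebo response, subjects who fail for a weak response may have fewer opioid effects, and the mix of failure reasons is not given. A reader might also infer that the broad reading corrupts the tables by CAM2038 dose. Only the Overall column could be affected.

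The primary efficacy analysis uses the Completer Population and does not depend on this definition.

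**What to change.** 1. In the protocol synopsis, Protocol 12.2 and SAP 5.0, define the Safety Population in identical words as subjects who received at least one CAM2038 injection. Use it for all tables by CAM2038 dose and Overall.
2. Add a Qualification Safety set: all subjects who received at least one Qualification-session challenge injection (0, 6 or 18 mg). Base Table 14.3.2 on it, with denominators by challenge dose received, and relabel the table in SAP Appendix A.
3. Summarise adverse events during IR morphine separately, among all subjects given at least one IR morphine dose. Protocol 12.3.4.1 calls for a morphine display, and Appendix A lists no table for it. Keeping it separate stops subjects who left before any challenge injection from diluting the hydromorphone rates.
4. If a like-for-like comparison with the Treatment Phase is wanted, also show the Qualification table for the CAM2038-treated subset, labelled as such.

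The cost is wording in three places, one population flag, one relabelled table and one further summary from dosing and event records already collected. No new data or change in conduct is needed. It should be settled before database lock.
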